Research Strategy

Sleep To Reduce Incident Depression Effectively (STRIDE)

NCT03322774

Date: 1/NOV/2017

Research Strategy

Sleep to Reduce Incident Depression Effectively (STRIDE)

Depression rates have remained largely unchecked in the US due to poor detection of risk for major depressive disorder (MDD), which leads to missed opportunities for primary prevention. However, one solution may be insomnia intervention, as people with insomnia disorder are at markedly high risk for incident depression. Furthermore, insomnia is the most frequent residual symptom domain that persists despite successful treatment of MDD, and is a predictor of relapse. As insomnia is a modifiable risk factor for depression, targeted insomnia treatment may reduce incident depression. As limited availability of sleep specialists is a barrier to nonpharmacological treatment of insomnia, integration of web-based technology with primary care services offers a novel solution. Along with our preliminary data, previous studies show that digital cognitive behavioral therapy for insomnia (*d*CBT-I) is an efficacious insomnia treatment, and the use of *d*CBT-I to prevent depression would be a novel application of this approach that is widely accessible, scalable and cost-effective for both patients and providers. The proposed intervention will leverage primary care as an entry point for early sleep intervention, as identification and treatment of both MDD and insomnia typically first occur in primary care.

We propose a large-scale clinical trial in primary care utilizing a stepped-care model to determine the *effectiveness* of *d*CBT-I alone or in combination with traditional face-to-face cognitive behavioral therapy for insomnia (CBT-I), and the effects of these established sleep interventions on the prevention of depression. This stepped care trial utilizes a “SMART” design by randomizing to internet-based *d*CBT-I or an attention-control group. Following this phase, a second randomization to face-to-face *clinician-based* CBT-I or attention control will be provided to patients who do not respond to *d*CBT-I. The present trial represents an innovative combination of these insomnia therapies with potential for real-world implementation and scalability. Another important and unique component of the trial is the 1-year follow-up assessment of participants to determine the durability of digitally- and traditionally-delivered behavioral insomnia treatments over time, and to fully assess the impact on prevention of incident depression and relapse.

The goals of this trial will be to 1) determine the relative *effectiveness* of *d*CBT-I alone or in combination with clinician-based CBT-I in non-depressed insomniacs and 2) to test the effects of these sleep interventions for preventing depression incidence and relapse. Moderators of the effects including sleep reactivity, rumination, race, and SES will be assessed.

We will deliver *d*CBT-I to individuals with insomnia disorder, and add face-to-face CBT-I for non-remitters. We will compare sleep outcomes and depression rates to a control group at post-treatment, and then at 1 year follow-up.

Aim 1a) Assess the acute and long-term effectiveness of *d*CBT-I on RDoC sleep parameters: Insomnia Severity Index (ISI), sleep onset latency (SOL) and wake after sleep onset (WASO) in an insomnia cohort including those at elevated-risk for depression (high sleep reactivity, low SES, minority). This aim will be tested by administering internet-based *d*CBT-I to people with insomnia and adding CBT-I in non-remitters (ISI > 10 or < 8 point ISI reduction), as well as comparing the RDoC sleep outcomes to an attention control group post-treatment and at 1 year follow-up.

Aim 1b) Determine the acute and long-term effectiveness of using face-to-face CBT-I to treat insomnia in non-responders on RDoC sleep outcomes (ISI, SOL, WASO) relative to a comparison group post-treatment and at 1-year follow-up.

Aim 2a) Determine the effects of *d*CBT-I and CBT-I using a stepped care model for prevention of **2a)** incident depression and **2b)** depression relapse. These aims will be tested by comparing the 1-year rate of depression outcomes of both *d*CBT-I and CBT-I to an attention control group.

Aim 3a) (Exploratory) Evaluate changes in nocturnal rumination as a modifiable behavior (post-treatment) that mediates the effect of insomnia treatment on subsequent depression-risk.

Aim 3b) (Exploratory) Determine the moderating effects of important depression risk-factors (race, SES) on the change in sleep and depression outcomes to establish the critical need and value of early risk-detection and prevention for these groups, and demonstrate the potential greater impact in terms of prevention for individuals with high sleep reactivity.

Figure 1: Study Overview

[figure not shown]
[figure not shown]

Figure 2: Study Timeline and Milestones

Research Strategy

We propose to enroll 500 trial participants (insomnia without depression) in alignment with ongoing data collection procedures within the HFHS network of sites in southeastern Michigan. Baseline assessment will include the utilization of standardized and validated assessment tools for insomnia and major depressive disorder.^{9,71,78-82} Following baseline assessment, insomnia participants will be randomized into Insomnia Treatment (T) or Attention Control (C) groups with a sample of no less than 250 per group, at which point the T group will receive their first treatment with the utilization of Sleepio (www.sleepio.com), an online cognitive behavioral therapy for insomnia *d*(CBT-I).⁸³ Participants will receive 6 weekly sessions of online *d*CBT-I. Specifically, participants are immersed in a fully automated media-rich web environment, driven dynamically by baseline and progress data. The C group will receive sleep hygiene education, which will serve as a credible placebo intervention as it mimics the web-based patient contact inherent in *d*CBT-I, but is inert with respect to sleep outcomes.⁸⁴ As with the *d*CBT-I group, these topics will be divided equally across 6-8 weekly sessions.

Those without insomnia remission following *d*CBT-I (ISI > 10)⁶⁸ treatment (typically 40%) will be randomized to standard face-to-face CBT-I treatment or attention control during this second phase of the SMART design. Treatments will be done at sites spread across the Detroit Tri-county area by psychologists certified in behavioral sleep medicine. For all groups, research assessments (sleep and depression) will be obtained at pre-treatment baseline, post-treatment 1 (~8 weeks following initiation of *d*CBT-I), post-treatment 2 (~8 weeks following face-to-face CBT-I initiation), and follow-up. The 1 year follow-up research assessments will include assessment of depression incidence and relapse occurring at any point throughout the previous 12-month period before the respective assessment. Moderation variables (i.e., sleep-reactivity, demographics) will be collected at baseline and mediation variables (i.e., nocturnal rumination) will be measured at each post-treatment and follow-up research assessment for all groups.

We will align with the following recommendations for effectiveness trials with minimal exclusion criteria to ensure a diversity of the sample representative of the population encountered in clinical practice.⁷⁵ We will only exclude those unwilling to participate, under the age of 18, those already on antidepressants, those already known to be harmed or not benefitted by one of the CBT-I interventions, known sleep disorders by EMR (e.g. sleep apnea, narcolepsy) and untreated medical or psychiatric disorders. Additionally, during the initial screening, those with depression (PHQ-9 or QIDS moderate) will be excluded.

Overall, we are assuming an attrition rate of approximately 30%, Although trial participants will be predominantly recruited through our network of primary care sites (31 in 2016), we will mitigate recruitment shortfalls through the HFHS Sleep Center patient registry (>20,000 insomnia patients). Participants will receive a stipend of \$20.00 per assessment and follow up.

We will also test treatment effects on quantitative sleep parameters including ISI, sleep onset latency (SOL), wake after sleep onset (WASO), and sleep efficiency collected using standardized report-based measures. Sleep diary data will be collected as part of the standard of care during each treatment to analyze trends across time.⁹¹ Depression outcomes will be measured by the 16-item Quick Inventory of Depressive Symptomatology (QIDS),⁷⁷ which is more extensive than the PHQ-9 and will be measured pre- and post-treatment during an online assessment following screening. As sleep is a component of the QIDS assessment, items relating to insomnia will be removed for all analyses (see below). Both study entry and case identification will include QIDS criteria for chronic nonpsychotic, major depressive disorder.⁷⁷ To enter the study participants will need to score less than an 11 on the QIDS. During year 1 follow-up, MDD cases will be identified (new onset, recurrence) for those who meet criteria of greater than or equal to 13 or a lower sub-threshold cut off greater or equal to 11 to increase sensitivity.^{77,82}

TARGETS

Rumination (mediator): refers to the perseveration of negatively-valenced thoughts, which critically increases risk for depression.⁹³ To test the possibility that insomnia-induced rumination serves as a risk factor for depression, we will include a state rumination measure at the post-treatment assessment to be used in a separate mediation model to test for the possibility that rumination is a primary component in the development of depression in individuals with insomnia. The target (mediator) in the proposed studies is state-rumination, specifically, nocturnal rumination which will be assessed using the Thought Control Questionnaire Insomnia-Revised (TCQI).⁹⁸ Whereas good sleepers get an adaptive reprieve from rumination at bedtime, insomnia extends rumination into the night.¹⁰⁶ Further, the inability to fall asleep at night can itself trigger negative schemas, such as helplessness and lack of control, that provide additional content for rumination.¹⁰⁷ While good sleepers think about '*nothing in particular*', insomniacs engage in nocturnal rumination about daytime stressors or the adverse effects of poor sleep. Insomnia may thus be a key contributor to nocturnal rumination.¹⁰⁸ Yet, no prior study has investigated rumination as a modifiable component of insomnia that when attenuated may lead to reduced MDD risk (Specific Aim 3).

Sleep reactivity¹²⁰(moderator): may moderate the effects of sleep improvement on depression. **Identifying a significant moderator(s) of treatment impact could lead to the development of cost-effective strategies to triage those at**

Research Strategy

greatest risk for depression into effective preventative programs of treatment. This directly aligns with NIMH's Strategic Objective 3, which is to identify focused and impactful *preventative* interventions. One risk factor linked to both insomnia and depression is the heritable trait of sleep reactivity.^{122,123} Sleep reactivity is a trait predisposition to insomnia that manifests as a *sleep system* that is over-sensitive or “over-reactive” to stress.¹²⁰ The Ford Insomnia Response to Stress Test (FIRST)¹²⁴ is a psychometrically and biologically validated instrument used to measure sleep reactivity. It is expeditious and cost-effective, minimizing burden in both research and clinical settings. Substantial evidence demonstrates reliability, validity, and utility for the FIRST. Longitudinal studies have shown high sleep reactivity (FIRST) increase the risk of new onset insomnia and predict the chronicity of insomnia in good sleepers up to 3 years later.^{24,132-134}

Aim 1: analysis will be on the post-treatment impact on RDoC sleep outcomes (ISI) and QIDS of the internet-based dCBT-I, followed by the more **personalized face-to-face** CBT-I group compared to the attention control group. Quantitative sleep measures, SOL and WASO, will also be assessed. A linear mixed model will examine the post-treatment sleep values using the baseline covariates. **Aim 2:** A comparison of face-to-face versus attention control will use an analogous statistical methodology as described above for Aim 1.

Aim 3: (rumination and sleep reactivity): To identify baseline and time-varying factors that predict the better second-phase intervention among non-remitters to Sleepio, Q-learning¹³⁸⁻¹⁴⁰ will be used. We will also generalize and apply mediator-analysis methodologies¹⁴¹ for examining the mechanisms of action by which the treatment groups exhibit their effects (i.e., targets). We will examine baseline predictors (e.g., sleep reactivity, race, SES) of change in outcomes (i.e., group x condition interaction) to establish the critical need for early risk-detection and prevention for highly reactive sleepers, and demonstrate the potential greater impact in terms of prevention for individuals with elevated risk factors (i.e., sleep reactivity, SES, race).

Assessment of reduction in suicidal behavior and related outcomes: Columbia-Suicide Severity Rating Scale (C-SSRS) will be included in all assessments. Appropriate action (ER referral, hospital admission, MH referral) will be taken as necessary, and C-SSRS data will be collected for supplementary analyses.

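### The face-to-face CBT-I contrast names no therapist effect, so its standard error will be too small if outcomes correlate within psychologist and the control arm has no therapist

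*Combined protocol and SAP*

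**What the plan says.** All references are to the combined protocol and SAP.

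- **Second-phase design** (Research Strategy, paragraph on those without remission after digital CBT-I). Patients without remission after digital "treatment (typically 40%) will be randomized to standard face-to-face CBT-I treatment or attention control during this second phase of the SMART design". The next sentence covers delivery: "Treatments will be done at sites spread across the Detroit Tri-county area by psychologists certified in behavioral sleep medicine". The number of psychologists and their caseloads are not given.
- **Attention control** (Research Strategy, enrolment paragraph). Only the first-stage control is described: "The C group will receive sleep hygiene education, which will serve as a credible placebo intervention as it mimics the web-based patient contact inherent in" the digital programme. The plan does not say how, or by whom, the second-stage control is delivered.
- **Analysis** (closing paragraphs on Aims 1 and 2). For Aim 1: "A linear mixed model will examine the post-treatment sleep values using the baseline covariates". For the second-stage contrast: "A comparison of face-to-face versus attention control will use an analogous statistical methodology as described above for Aim 1". That paragraph is labelled Aim 2, but in the list of aims the face-to-face comparison in non-responders is Aim 1b and Aim 2 concerns depression.

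The plan mentions no therapist or site effect, no ICC, no cluster-robust standard error, and no recording of the treating psychologist.

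**The concern.** Patients treated by the same psychologist tend to have more similar outcomes than patients treated by different ones. If that holds here, the face-to-face arm carries less independent information than its head count suggests. If the control is web-based, as in the first stage, its patients are not grouped in this way. The design is then partially nested: one arm is clustered and the other is not.

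A model with baseline covariates alone does not capture this. A patient-level random effect for repeated visits would not capture it either, because the correlation lies between patients of one psychologist and not within a patient over time.

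The contrast at stake asks whether adding clinician CBT-I helps patients whom the digital programme did not bring to remission. It is the smaller of the trial's two randomized comparisons. An understated standard error would make a false claim of benefit more likely and would give confidence intervals that are too narrow.

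**Working it through.** **Plan's own figures.** The plan gives no power, alpha, effect size, standard deviation or ICC, so there is no sample-size result to reproduce. The only check available is 2 × 250 = 500, which agrees with the stated enrolment.

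**Inputs from the plan**
- First stage: "randomized into Insomnia Treatment (T) or Attention Control (C) groups with a sample of no less than 250 per group".
- Share entering the second phase: 40%, described as typical.
- Attrition: "Overall, we are assuming an attrition rate of approximately 30" percent.

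**Assumptions, not in the plan**
- 1:1 second-stage allocation and a two-sided 5% test.
- K = 3 to 8 psychologists with equal caseloads.
- Therapist ICC of 0.02 to 0.10.
- No therapist in the control arm, and equal total variance in the two arms.
- The 30% attrition applies to the second-stage arms.

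**Step 1: arm size.** 250 × 0.40 = 100, so n = 50 per arm. After attrition, 50 × 0.70 = 35 per arm.

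**Step 2: formulas**
- Caseload: m = n / K.
- Design effect in the face-to-face arm: DE = 1 + (m − 1) × ICC.
- True SE / naive SE: R = √((1 + DE) / 2).
- Actual type I error: 2 × (1 − Φ(1.96 / R)).

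**Step 3: results**

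| n per arm | K | ICC | m | DE | R | Type I error (formula) |
|---|---|---|---|---|---|---|
| 50 | 8 | 0.02 | 6.25 | 1.105 | 1.03 | 5.6% |
| 50 | 5 | 0.05 | 10.0 | 1.450 | 1.11 | 7.7% |
| 50 | 3 | 0.10 | 16.7 | 2.567 | 1.34 | 14.2% |
| 35 | 8 | 0.02 | 4.375 | 1.068 | 1.02 | 5.4% |
| 35 | 5 | 0.05 | 7.0 | 1.300 | 1.07 | 6.8% |
| 35 | 3 | 0.10 | 11.7 | 2.067 | 1.24 | 11.4% |

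Simulation of the naive t-test with 40,000 runs per setting agrees: 5.5%, 7.8% and 13.9% for the three rows at 50 per arm, and 5.5%, 6.9% and 11.6% at 35 per arm.

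**Step 4: limits.** At ICC = 0, DE = 1, R = 1 and the error is 5.0%. With 10 psychologists and an ICC of 0.01 at 50 per arm, DE = 1.04, R = 1.01 and the error is 5.2%.

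**Step 5: cost of the correct analysis.** With Satterthwaite degrees of freedom at the true variances, df = (DE + 1)² / (DE² / (K − 1) + 1 / (n − 1)). The interval widens by the factor R × t(df) / t(2n − 2). At 50 per arm, t(98) = 1.984.
- K = 8, ICC 0.02: df = 22.7, t = 2.070, factor 1.026 × 2.070 / 1.984 = 1.07.
- K = 5, ICC 0.05: df = 11.0, t = 2.201, factor 1.107 × 2.201 / 1.984 = 1.23.
- K = 3, ICC 0.10: df = 3.8, t = 2.823, factor 1.335 × 2.823 / 1.984 = 1.90.

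**Step 6: can the therapist variance be estimated?** In simulation with 5 psychologists and an ICC of 0.05, the between-therapist variance estimate was zero or negative in about 37% of runs at 50 per arm and 43% at 35 per arm. A Satterthwaite test at therapist level nevertheless brought the error back to about 5% with 5 or more psychologists.

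**The case against.** A reader might infer that the standard error is certainly too small, that therapists are few, and that the plan treats all patients as independent. The documents support none of these as fact.

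- **Size is unknown.** No ICC, number of psychologists or caseload is given, and at an ICC of zero nothing is wrong. This stands, so the claim is conditional and its size is a range. The stated attrition also lowers caseloads, and with them the inflation.
- **Control delivery is not described.** The web-based description belongs to the first stage. The sentence about psychologists follows one that names both second-stage options, so it could be read to cover both. If the same psychologists served both arms, a shared therapist effect would largely cancel from the contrast. In simulation with 5 psychologists, an ICC of 0.05 and 50 per arm, the naive test then had a type I error just under 5%. A random effect in the face-to-face arm alone would be the wrong model. This also stands. The web-based reading is more plausible, because the overview calls only the face-to-face option clinician-based, but it remains an inference.
- **The therapist term is unspecified, not excluded.** A linear mixed model has some random effects, and the plan lists none. That is true, but baseline covariates are all it names, so nothing commits the analysis to a therapist effect.
- **The remedy is costly and imperfect.** With few psychologists the variance is poorly estimated and intervals can widen a great deal. That is a reason to prespecify a fallback. It does not justify leaving the correlation out.

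**Conclusion.** The point holds in conditional form. The face-to-face arm is delivered by psychologists, and the model for its comparison with control names no therapist effect. If outcomes correlate within psychologist and the second-stage control has no therapist, the standard error of this contrast will be too small.

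Over the assumed range, the inflation runs from slight to material: type I error of about 5.5% to 14% at 50 per arm, and about 5.5% to 11% at 35 per arm. The documents do not show where in that range the trial falls, or that it falls there at all. They do not support saying that the standard error is wrong as a matter of fact. What they do show is a foreseeable source of correlation with no stated plan for it, in the smaller of the two randomized comparisons. It should be settled before analysis. Confidence is medium because the ICC, the number of psychologists and the delivery of the control are all missing.

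**What to change.** 1. Record the treating psychologist for each second-stage patient. If this is not captured during the trial, adjustment may be impossible later.
2. State how many psychologists are expected, and who delivers the second-stage attention control.
3. Match the model to that answer. If only the CBT-I arm has therapists, prespecify a partially nested mixed model: a random therapist effect in the CBT-I arm, arm-specific residual variances, and Kenward-Roger or Satterthwaite degrees of freedom. If psychologists deliver both arms, use a therapist effect crossed with arm instead.
4. Because the therapist variance is poorly estimated with few psychologists, add a sensitivity analysis at fixed ICC values, for example 0, 0.02, 0.05 and 0.10.
5. Align the aim label of this contrast between the list of aims and the analysis paragraph.

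**Cost.** One extra data field and some SAP wording. The statistical price is wider confidence intervals for this contrast. At 50 per arm they are about 7% wider with 8 psychologists and an ICC of 0.02, about 23% wider with 5 and 0.05, and up to about 90% wider with 3 and 0.10. The loss of precision can be substantial, and the sponsor should know this before the number of psychologists is fixed.

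### Nocturnal rumination has no stated pre-treatment measurement, so the exploratory mediation aim (Aim 3a) lacks its own baseline for dCBT-I versus control

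*Combined protocol and SAP*

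**What the plan says.** The assessment schedule in the Research Strategy treats two kinds of variable differently. For moderators: "Moderation variables (i.e., sleep-reactivity, demographics) will be collected at baseline". For mediators: "mediation variables (i.e., nocturnal rumination) will be measured at each post-treatment and follow-up research assessment for all groups". The Targets section, under Rumination (mediator), repeats the later timing: "we will include a state rumination measure at the post-treatment assessment". The preceding paragraph on outcomes places the QIDS on both sides of treatment: it "will be measured pre- and post-treatment during an online assessment following screening".

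The research assessments that include the pre-treatment baseline are described as covering sleep and depression, and the baseline tools named are for insomnia and major depressive disorder. Rumination appears in neither description.

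Two statements point the other way. Aim 3a, labelled exploratory, is to "Evaluate changes in nocturnal rumination as a modifiable behavior (post-treatment) that mediates the effect of insomnia treatment on subsequent depression-risk". The goals paragraph of the aims says "Moderators of the effects including sleep reactivity, rumination, race, and SES will be assessed", which makes rumination a moderator, and moderators are the variables collected at baseline.

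**The concern.** Mediation has two links. The first, treatment to rumination, is randomised, so comparing post-treatment TCQI between arms is unbiased without a baseline, only less precise. The second, rumination to later depression, is not randomised. People who ruminated more before treatment may both ruminate more afterwards and become depressed more often, and that pattern can look like mediation even if lowering rumination does nothing for depression. The Targets section itself presents rumination as a depression risk factor, so prior rumination is a plausible confounder on the plan's own premise.

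Without a pre-treatment TCQI, the dCBT-I versus control analysis can neither compute within-person change from pre-treatment nor adjust the second link for the most direct confounder. Baseline QIDS removes part of the problem; how much depends on how closely it tracks rumination. Once treatment has begun, the missing value cannot be obtained.

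**Working it through.** **Plan's own figure.** There is none. The plan gives no power, effect size, event rate or correlation for Aim 3a, so everything numerical below is a sensitivity range.

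**Inputs from the documents.** 500 enrolled, at least 250 per group, about 30% attrition, and typically 40% non-remission after dCBT-I.
- Completers: 500 x 0.70 = 350, or 175 per arm.
- Second randomisation: 0.40 x 250 = 100 people, or 0.70 x 100 = 70 if all attrition came first. These people have a TCQI at post-treatment 1, before their second randomisation, so the gap does not extend to face-to-face CBT-I versus control.

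**Assumptions, not in the documents.** Two-sided 5% test; baseline-to-post TCQI correlation r1 = 0.4-0.6; baseline TCQI-to-depression correlation r2 = 0.2-0.3; baseline QIDS-to-depression correlation 0.4; baseline QIDS-to-TCQI correlation rho = 0.5 or 0.2; depression incidence 10% or 20%.

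**Step 1: what confounding is left after adjusting for QIDS.** The direct coefficient of baseline TCQI on latent depression, given QIDS, is (r2 - 0.4 rho) / (1 - rho^2).
- rho = 0.5, r2 = 0.2: (0.2 - 0.20) / 0.75 = 0.000
- rho = 0.5, r2 = 0.3: (0.3 - 0.20) / 0.75 = 0.133
- rho = 0.2, r2 = 0.2: (0.2 - 0.08) / 0.96 = 0.125
- rho = 0.2, r2 = 0.3: (0.3 - 0.08) / 0.96 = 0.229

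QIDS therefore suffices in the first case and not in the others.

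**Step 2: false-positive rate of the rumination-to-depression path.** Simulation with n = 350, 8,000 trials per cell, no true effect of treatment or post-treatment rumination on depression, and a logistic model with arm, post-treatment TCQI and baseline QIDS. Depression is a latent normal variable cut at the stated incidence.

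| r1 | r2 | rho 0.5, 10% | rho 0.5, 20% | rho 0.2, 10% | rho 0.2, 20% |
|---|---|---|---|---|---|
| 0.4 | 0.2 | 4.9% | 5.1% | 8.1% | 10.1% |
| 0.5 | 0.2 | 5.1% | 5.1% | 10.4% | 12.2% |
| 0.5 | 0.3 | 8.8% | 10.4% | 23.7% | 32.5% |
| 0.6 | 0.3 | 11.0% | 13.6% | 32.5% | 43.2% |

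The median spurious odds ratio per SD of post-treatment rumination is 1.00-1.15 at rho = 0.5 and 1.10-1.34 at rho = 0.2.

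**Step 3: variations.**
- Both links required to be significant, with an assumed 0.25 SD treatment effect on rumination: 3.2-9.2% at rho = 0.5 and 5.3-28.0% at rho = 0.2.
- Baseline TCQI added as covariate: 4.8-5.4%, or 4.8-7.0% if its reliability is 0.8.
- Entry limit on depression ("To enter the study participants will need to score less than an 11 on the QIDS") mimicked by cutting the QIDS distribution, 4,000 trials per cell. Cut at an assumed 70th percentile: 4.7-14.1% and 8.4-45.1%. Cut at the 50th: 5.0-14.5% and 8.3-47.8%. The limit changes little.

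**Step 4: precision of the treatment-to-rumination path.** SE = sqrt(4(1 - k^2)/350), where k is the correlation of the covariate with post-treatment TCQI. Power is for a 0.25 SD effect.
- No covariate, k = 0: SE 0.107, power 65%.
- Baseline QIDS, k = r1 x rho = 0.08 to 0.30: SE 0.107 to 0.102, power 65-69%.
- Baseline TCQI, k = 0.4, 0.5, 0.6: SE 0.098, 0.093, 0.086, power 72%, 77%, 83%.

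**The case against.** The strongest reply is that silence is weak evidence in so short a document. Its lists are plainly incomplete: the plan says "Columbia-Suicide Severity Rating Scale (C-SSRS) will be included in all assessments", yet neither description of the baseline mentions that scale. Figures 1 and 2 are not available and could show a baseline TCQI. Rumination is called a moderator in the goals, and the Aim 3 analysis paragraph pairs it with sleep reactivity before mentioning baseline factors. This stands to the extent that a baseline TCQI cannot be ruled out. It does not supply one: the baseline moderator list leaves rumination out, and the baseline factors in the Aim 3 paragraph serve the second-phase question among non-remitters, where post-treatment 1 would do. Even if a baseline was intended, the passages disagree.

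A second reply is that a between-arm difference after treatment already expresses a treatment-induced change, so no change score is needed. That is right for the randomised link and does not help the other one.

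A third is that the magnitude rests wholly on assumed correlations, that its upper end needs a weak QIDS-TCQI correlation together with the stronger TCQI-depression correlation, and that only QIDS was adjusted for. All of this stands. At an intermediate QIDS-TCQI correlation of 0.35 the single-path error is about 6-27%, and about 4-17% when both links must be significant, which is nearer to a mediation claim. Baseline sleep measures and sleep reactivity might lower these figures by an unknown amount.

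Finally, the aim is exploratory and its mediation method is described only in general terms. That limits the consequence but does not remove it.

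**Conclusion.** The point holds, with medium confidence because the figures cannot be seen. On the stated schedule, Aim 3a for dCBT-I versus control has no pre-treatment rumination value: no change from pre-treatment, no adjustment of the non-randomised path for prior rumination, and lower power on the randomised path. The inflation of false mediation findings could be nil or large. The documents do not allow a narrower statement, because it depends on how well baseline QIDS stands in for baseline rumination. The primary sleep and depression comparisons are untouched, as is the second randomisation. What makes this worth acting on is that the remedy is small and the omission irreversible for each participant once treatment starts.

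**What to change.** In the assessment schedule, add the TCQI at pre-treatment baseline, before the first randomisation, alongside the later time points already listed, and make the Targets section agree. If it is already collected at baseline, state that. In addition:

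- For dCBT-I versus control, include baseline TCQI and baseline QIDS as covariates in both the mediator model and the outcome model of Aim 3a.
- For the second randomisation, use the post-treatment 1 TCQI as the baseline.
- Reconcile the goals paragraph, the schedule, the Targets section and the Aim 3 analysis on whether rumination is a moderator, a mediator or both.
- State that baseline adjustment reduces mediator-outcome confounding but does not remove it.
- For anyone randomised without a baseline TCQI, adjust for baseline QIDS, ISI and sleep reactivity, and report the path as open to confounding by prior rumination.

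The cost is one more questionnaire in a pre-treatment online assessment that the plan already describes. The downside is a small added burden on participants; the documents do not give the length of the TCQI.
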